## MEDICAL PROTOCOL (HRP-590)

PROTOCOL TITLE: Brivaracetam to Reduce Neuropathic Pain in Chronic SCI: A Pilot Clinical Trial  
VERSION DATE: 03/18/2024

numerical rating scale has been recommended by the IMMPACT consensus group for use in pain clinical trials [Dworkin et al., 2005] and by the 2006 NIDRR SCI Pain outcome measures consensus group. [Bryce et al., 2007] This scale is recommended to standardize pain outcomes across studies. The International Spinal Cord Injury Pain Data Set also assesses dimensions of pain (i.e. intensity of pain, time of day, location, occurrence, etc.), and pain interference with mood, activity, and sleep.

*Assessment of Mood with the Patient Health Questionnaire (PHQ-9).* This is a 9-item scale that assesses patient quality of life through mental state. It identifies active suicidality. [Kroenke et al., 2001] It assists physicians in both diagnosing depression and determining a treatment route. It incorporates DSM-IV depression classifications and determines severity of depression. [Bombardier et al., 2004; Graves and Bombardier, 2008; Kalpakjian et al., 2009; Krause et al., 2010]

*Satisfaction with Life Scale (SWLS).* This is a 5-item scale that assesses patient happiness with current quality of life. [Diener et al., 1985] It consists of a 1-7 simple Likert scale.

*Pittsburgh Sleep Quality Index.* This is a 9-item scale that assesses sleep quality.

*Tampa Scale for Kinesiophobia.* This is a 17-item scale that assesses fear of movement.

*Craig Handicap Assessment and Reporting Technique – Short Form (CHART-SF).* This assessment is commonly used to provide an objective measure as to the degree by which a person with SCI remains with impairment or disability [Whiteneck et al., 1992]. It measures several domains including: the type and level of daily assistance needed on both a physical and cognitive level (i.e. personal care, hygiene, decision making, communicating with others); level of physical activity (ranging from travel to daily mobility); transportation needs how time is spent (i.e. employment, housekeeping, cooking, leisure activities); social interactions (including relatives, co-workers, and friends); and available financial resources.

*DN4 Assessment Tool.* This is a 4-item assessment that characterizes neuropathic pain.

MEDICAL PROTOCOL (HRP-590)

PROTOCOL TITLE: Brivaracetam to Reduce Neuropathic Pain in Chronic SCI: A Pilot Clinical Trial  
VERSION DATE: 03/18/2024

*Moorong Self-Efficacy Scale (MSES)*. This is a 16-item scale that assesses self-efficacy in performing functional activities of daily living individuals with SCI.

*Pain Catastrophizing Scale (PCS)*. This 13-item self-report measure is designed to assess catastrophic thinking related to pain among adults with or without chronic pain.

*Perceived Disability Index (PDI)*. This is a brief, self-report instrument developed to assess self-perception of disability.

*Penn Spasm Frequency Scale (PSFS)*. This is a self-report measure that assess a patient's perception of spasticity frequency and severity following a spinal cord injury.

*Intervention Expectations*. This self-report will assess what participants expect their outcomes to be during and after their participation in the study.

*Concurrent Pain Medication Use*. Although pain medications can confound the analgesic effects of brivaracetam, we consider it to be unethical to require participants to discontinue pharmacologic treatment for pain over the course of the study as a criterion for enrollment. In addition, to increase generalizability, it is important to recruit participants using pain medications. Therefore, we will record pain medication use over the course of the trial and consider this in the analysis.

*Pain Intensity and Medication Use Diary*. We will monitor daily pain reports and patient medication throughout the course of the study using a Pain Intensity and Medication Use Diary. Participants will be asked to record daily pain ratings (highest pain 0-10, lowest pain 0-10, and average pain 0-10) and any pain medication use. This diary will be started 1 week prior to drug treatment and maintained until completion of the study.

*Assessment of Cortical Activity by Brain MRI*. MRI scans of the brain will be performed for participants who are eligible and provide consent to MRI. Testing will be performed at baseline and end of study. We will use 3 Tesla Magnetic Resonance Imaging to collect i) brain structure (Multi Echo Magnetization Prepared Rapid Acquisition Gradient Echo, MEMPRAGE) ii) brain white matter integrity (Diffusion Weighted Imaging, DWI), iii) brain resting state functional connectivity (resting state functional Magnetic Resonance Imaging, rsfMRI), and iv) evoked responses to Motor Imagery

**MEDICAL PROTOCOL (HRP-590)****PROTOCOL TITLE: Brivaracetam to Reduce Neuropathic Pain in Chronic SCI: A Pilot Clinical Trial**  
**VERSION DATE: 03/18/2024**

(MI). MI involves asking individuals to envision themselves executing motor actions, without actual execution, a task that activates the same or similar neural systems as the actual execution of motor actions.

*Limited safety labs for hepatic cirrhosis, renal insufficiency, and pregnancy.*  
At the final study visit, participants will complete a fasting blood draw either at the Clinical Research Unit or through their primary care provider. Blood will be analyzed for blood urea nitrogen (BUN), creatinine, alanine transaminase (ALT), aspartate transaminase (AST), total bilirubin, albumin, GFR, calcium, corrected calcium, and human chorionic gonadotropin (hCG); urine hCG test will also be accepted. INR will be collected at the discretion of the participant's primary care provider if the participant is on anticoagulation or has abnormal LFTs. People who are menopausal and have not had a menstrual period for at least 12 months, or people who have had a hysterectomy will not be required to take pregnancy tests. Results of the pregnancy test will be sent only to the study staff by the CRU staff.

**Table 1. Study Procedures**

Study Task	Pre-Screen	Visit 1*	Visit 2*	Visits 3 (end of study testing)	2 weeks drug dose reduction (after end of study testing)	Visit 4 (long-term follow-up)
Pre-Screening Phone Survey	X					
Consent/randomization		X				
MRI Brain Scan (optional)			X	X		
Blood draw for biomarkers (optional)			X	X		
Physical health exam, health history screening, surveys		X		X		X
Initiate intervention			X			
Dispense 3-month drug supply			X			
Reminder check-in: begin 2-week drug dose reduction protocol after end of study testing					X	
Limited safety labs (blood draw, required)				X		
Pill count/medication diary review					X	
Pregnancy test (for women of child-bearing potential)				X		
Adverse Events	Assessed weekly (phone)					

\*Visits 1 and 2 may be combined for participant convenience

## MEDICAL PROTOCOL (HRP-590)

PROTOCOL TITLE: Brivaracetam to Reduce Neuropathic Pain in Chronic SCI: A Pilot Clinical Trial  
VERSION DATE: 03/18/2024

---

\*\*Medical clearance must be clinically obtained from participants' primary care provider or other healthcare provider within 1 month prior to visit 1

*Study drop criteria.* Participants will be removed from the study for safety reasons including drug intolerance, drug allergy, drug contraindications, development of depression, aggressive behavior, anxiety, or suicidality, or evidence of brivaracetam adverse events according to the manufacturer's prescribing guide (package insert). Poor drug compliance will be recorded for consideration during the analysis but will not be cause for removal from this study. In the case of drug intolerance, participants will reduce the drug dose under medical supervision of the PI until the drug can be safely discontinued.

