## MEDICAL PROTOCOL (HRP-590)

PROTOCOL TITLE: Brivaracetam to Reduce Neuropathic Pain in Chronic SCI: A Pilot Clinical Trial  
VERSION DATE: 03/18/2024

asked to verify by phone or email receipt of study drug and initiation of the treatment course.

Drug dosage will be individually titrated for each participant with a goal of 100mg BID according to the following dose escalation protocol that we use clinically: 50mg BID X 2 weeks followed by 50mg TID X 2 weeks followed by 100mg BID X for 48 days, as tolerated. Participants will be allowed to reduce the dose of brivaracetam if they experience unacceptable side effects defined as increased somnolence according to routine clinical practice with other drugs in this class used for pain.

In the case of intolerance at 50mg BID during dose escalation, the dose will be reduced to 25mg daily or 25mg BID. In the case of intolerance, the dose will be reduced down 1 step to last tolerated dose. For intolerance at 100mg BID, the dose will be reduced to 50mg TID. For intolerance at 50mg TID, the dose will be reduced to 50mg BID. A dose of 50mg BID or higher must be maintained to complete the trial.

Drug discontinuation at study completion will be done according to the following protocol we use clinically that will be initiated for 2 weeks after end of study testing: Reduction to 50mg BID X 1 week followed by 50mg daily X 1 week. For those at the highest study tolerated dose of 50mg BID, the dose will be reduced to 50mg daily X 1 week and then stopped. At the end of study participants will be asked to mail empty bottles for pill counts with self-addressed and prepaid packaging, and will review the medication diaries via phone. We will use the clinically meaningful reduction in Brief Pain Inventory score of 1 point or more as the definition of “drug response” in this study. University of Minnesota Investigational Drug Services (IDS) will register the study, while Rx Artisans will be dispensing the drug.

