## **12.0 Withdrawal of Participants**

### *12.1 Withdrawal Circumstances:*

At any time after enrollment, a participant may be discontinued. Reasons for discontinuation of a participant from the study will include, but may not be limited to, the following:

- The participant is found to be intolerant to a required study procedure at any time point
- Failure of the participant to adhere to protocol requirements
- The participant experiences a serious adverse experience at any time point
- The participant develops an inter-current illness that would, in the judgment of the investigator, affect assessments of clinical status to a significant degree.
- The participant enrolls in another investigational study
- The participant requests to withdraw from the study

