### *12.3 Termination Procedures:*

Participation may be terminated due to drug intolerance or allergy and based on clinical judgement of the study team. All data collected will be retained and analyzed unless the participant specifically requests to have their data withdrawn from the analysis.

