### 18.2 Data Safety Monitoring

Plan for Monitoring Safety. The safety environment of UMN participants will be overseen and monitored by [name]. We will monitor to assure that participants meet eligibility criteria; that the informed consent process is conducted appropriately, that the data will be collected and analyzed as specified in the protocol, that adverse events (defined below) are reviewed promptly and reported as required (detailed below), that dropouts are documented, and that primary and secondary endpoints are evaluated. According to the data safety-monitoring plan, study participation will be terminated immediately in the event of injury or increased morbidity (drug intolerance). Data and all procedures will be monitored at each measurement time point and monthly throughout the duration of the study to ensure the safety of participants.

Unblinded Study Physician/Medical Monitor. Our safety monitoring plan also includes an independent medical monitor: [name] (Thomas Jefferson University). [name] will review all reported adverse events on a monthly basis and as needed with the PI, [name], who will inform [name] immediately of all study-related unanticipated problems involving risk to volunteers or others, serious adverse events, and all volunteer deaths associated with the protocol, and provide an unbiased written report of the event to the IRB and FDA. The medical monitor will comment on the outcomes of the event or problem, and in the case of a serious adverse event or death, comment on the relationship to

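### The sections on drug intolerance conflict on whether participation ends, and none requires a 3-month BPI after removal or says how a missing one is handled

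*Combined protocol and SAP*

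**What the plan says.** Four places deal with intolerance.

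- Section 4.1 (Description): "In the case of intolerance, the dose will be reduced down 1 step to last tolerated dose". It adds "A dose of 50mg BID or higher must be maintained to complete the trial", although it also provides for reduction below that level during escalation.
- Section 5.2 (Study drop criteria): "Participants will be removed from the study for safety reasons including drug intolerance, drug allergy, drug contraindications, development of depression". The dose is then reduced under supervision until the drug is stopped.
- Section 12.3: "Participation may be terminated due to drug intolerance or allergy and based on clinical judgement of the study team". The next sentence keeps all collected data in the analysis unless the participant asks for them to be withdrawn.
- Section 18.2: "study participation will be terminated immediately in the event of injury or increased morbidity (drug intolerance". The same section asks "that dropouts are documented".

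On outcome collection, section 5.2 places the end-of-study assessments 3 months after baseline and again 1 month after study medication ends. Table 1 has surveys at Visits 1, 3 and 4. The weekly calls are described as covering adverse events and the PHQ-9. Section 12.2 (Withdrawal Procedures) covers only a safe taper.

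On analysis, section 15.1 compares pain reduction by linear regression on group, time and their interaction, using baseline and 3 months. Section 3.1 defines response as a BPI fall of at least 1 point. Sections 15.1 to 15.3 name no analysis population and no missing-data method.

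**The concern.** Whether an intolerant participant stays in the trial depends on which section is followed. Under the drop criteria and section 18.2 as written, that person leaves the study, not only the drug, and nothing requires a pain score at 3 months.

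The triggers for removal (intolerance, allergy, depression, aggression, anxiety, suicidality) largely repeat the risks of the drug listed in section 13.1. Removal may therefore be more common on active drug, and those removed may differ from those who stay. The pilot exists to supply effect sizes and standard errors for a larger trial (sections 1.1 and 15.2). A bias from selective removal would pass into that sample size, and the standard error would not reveal it.

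**Working it through.** **1. The sections side by side**

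| Section | On intolerance | Does participation end? |
|---|---|---|
| 4.1 | Step the dose down | No, but a minimum dose is needed to complete |
| 5.2, drop criteria | Remove from the study, reduce until stopped | Yes, mandatory |
| 12.3 | Clinical judgement | Possibly |
| 18.2 | Terminate immediately | Yes, mandatory and at once |

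These cannot all apply to the same participant.

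**2. What a removed participant contributes.** The section 15.1 model has group, time and their interaction, so it fits four cell means. On all available rows the interaction equals the difference between arms in available 3-month means, minus the difference in all baseline means. A simulated data set (10 per arm, three active-arm 3-month values deleted) confirmed this: the interaction was −0.681, the same as that difference of means, against −0.680 from complete pairs alone. Retaining collected data therefore keeps the baseline of a removed participant but supplies no endpoint.

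**3. Illustrative size.** The documents give no dropout rate, effect size or SD, so there is no stated figure to reproduce and every share here is assumed. Let q be the share of the active arm removed and D the mean benefit over placebo in those who stay. Suppose that removed active participants had no benefit and that placebo removal is unrelated to pain.

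- Effect in all randomised: (1 − q)D
- Effect in those with a 3-month value: D
- Relative overstatement: 1/(1 − q) − 1

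| q | Calculation | Too large by |
|---|---|---|
| 10% | 1/0.90 − 1 | 11% |
| 20% | 1/0.80 − 1 | 25% |
| 30% | 1/0.70 − 1 | 43% |

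If those removed had half the benefit, the formula becomes 1/(1 − 0.5q) − 1, which gives 5%, 11% and 18%. If they had equal benefit, it gives zero. If the participants removed from placebo are the ones with worse pain, and this selection is stronger on placebo than on active, the bias can run the other way.

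**4. Scale against sampling error.** Section 5.1 gives 20 participants per site at two sites, and section 23.1 gives 20 study-wide, so equal arms would be 20 or 10. Assume a true effect of 0.5 SD.

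- At q = 20%, the bias is 0.25 × 0.5 = 0.125 SD. The standard error is √(1/8 + 1/10) = 0.47 SD, or √(1/16 + 1/20) = 0.34 SD.
- At q = 30%, the bias is 0.43 × 0.5 = 0.21 SD. The standard error is √(1/7 + 1/10) = 0.49 SD, or √(1/14 + 1/20) = 0.35 SD.

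**5. Responder status.** Assume 10 on active, 2 removed, and 4 responders among the other 8. Response is 4/8 = 50% in completers, 4/10 = 40% if those removed count as non-responders, and 6/10 = 60% if they count as responders. The plan does not say which applies, and Aim 2 compares imaging between active responders and non-responders.

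**The case against.** The strongest defence is that the sections can be read in sequence: step-down for intolerance of a dose level, removal for intolerance of the drug, and non-completion implied below the minimum in section 4.1. The general 3-month schedule might also cover anyone still in the study. This reading is possible, but the documents do not state it. It does not fit the immediate termination in section 18.2, and the drop criteria mention no earlier step-down. Nothing says that the 3-month assessment continues after removal. It is also fair that this is a pilot aimed at estimation, that all the bias figures are assumed, and that the separate protocol at the second site cannot be checked.

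Three stronger readings are tempting and should not be drawn.

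- A reader might infer that there is no analysis rule at all for removed participants. Section 12.3 does keep and analyse their collected data. What is missing is narrower: the analysis set, and the handling of an absent 3-month BPI or responder status.
- A reader might infer that the plan overstates benefit. The documents fix neither the sign nor the size of any bias.
- A reader might see a further conflict between "Poor drug compliance will be recorded for consideration during the analysis but will not be cause for removal from this study" in section 5.2 and "Failure of the participant to adhere to protocol requirements" in section 12.1. Section 12.1 is permissive and concerns protocol requirements in general, while section 5.2 is a specific exception for drug compliance. The two can coexist.

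**Conclusion.** The point holds in two parts. The sections on intolerance conflict on whether participation ends. Where removal is applied as written, no section requires a 3-month BPI or says how its absence, or missing responder status, is handled. The estimated effect then rests at 3 months on those who have a value.

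Whether this biases the result depends on how many are removed from each arm and how they fared, which the documents do not say. The 11%, 25% and 43% figures hold only for the assumed 10%, 20% and 30% active-arm removal, with no benefit in those removed and placebo removal unrelated to pain. In this pilot such a bias is probably smaller than the sampling error. It should still be corrected, because the estimate is meant for planning the next trial and the remedy is cheap.

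**What to change.** 1. Reconcile section 4.1, the drop criteria in section 5.2, section 12.3 and section 18.2. Which clinical rule applies is for the sponsor and clinicians.
2. State in the drop criteria and in sections 12.3 and 18.2 that stopping study drug, or ending treatment for safety, does not by itself end outcome collection. The BPI is then collected, remotely if needed, 3 months after baseline (the date section 5.2 already sets) unless consent is withdrawn.
3. In section 15.1, analyse all randomised participants by assigned arm. For a missing 3-month BPI, add a sensitivity analysis, fixed before unblinding if the blind is still intact, that spans no change from baseline and the placebo-arm mean change. Count missing responder status as non-response in a sensitivity analysis. Entry requires daily average pain of 9 or 10 (section 8.1). If the BPI score analysed starts at a similar level, no change is close to the worst case and should not stand alone.
4. Report removals by arm and reason.

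The cost is a short amendment and a remote questionnaire. The revision history records enrolment as complete at this version, so item 2 helps only participants not yet past their 3-month date, possibly few or none. Items 3 and 4 need no new data. The resulting estimate may be smaller, and the imputations can understate benefit.

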#### **3.2 Secondary Endpoint(s)/Event(s)/Outcome(s):**

Secondary outcomes include brain resting state functional connectivity and various psychosocial factors related to participants' experiences with SCI, such as change in mood, satisfaction with life, and community integration.

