CDE-recommended questionnaires relating to pain, mood, active suicidality, satisfaction with life, kinesiophobia, sleep quality, and community integration will be administered. Participants will then begin 3 months of active treatment (100 mg BID) or placebo. All participants will receive a medication diary to track study drug compliance and to record medication use. Blinded data collectors will perform weekly check-in calls to assess for medication-related adverse events including the PHQ-9 for changes in mood and suicidality. Reported AEs identified in these calls will be documented and immediately shared with the PI for review.

End of study assessments will be repeated 3 months after baseline testing and again 1 month after cessation of study medication (active/placebo).

Lab work will be repeated to confirm normal renal function, absence of liver cirrhosis, and absence of pregnancy in individuals of childbearing potential at the end of the study. Specimen collection and analysis will either occur at the Fairview Clinical Research Unit or with the participant's

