### *15.1 Data Analysis Plan:*

For aim 1, the main outcome variables of interest include various dimensions of pain, mood (PHQ-9), life satisfaction (SWLS), resting state brain connectivity, and community integration (CHART-SF) measured at baseline and again at 3-months of treatment. Of particular interest is whether there is a difference in pain reduction from baseline to end of study between the treatment and control groups; this will be analyzed in this pilot with linear regression including terms for group and time and the interaction of group by time. We note that many of these instruments have bounded scores and we will include analyses that recognize these (via, e.g., non- linearities or recognize the bounds such as Tobit regression) Further exploratory analyses will examine the relationships (correlations) between changes in pain and changes in mood, life satisfaction, resting state brain connectivity, and community integration using linear regression.

For aim 2, we will use the same analytic approach we have refined in our 2 active rsfMRI studies. MRI data will be analyzed using the SPM12 based Conn toolbox 3 (Version 17f, Matlab R2018b). Preprocessing steps include realignment and unwarping, slice-timing correction, ART based identification of outlier scans for scrubbing, segmentation and normalization to MNI space, and 8 mm smoothing. Denoising steps include scrubbing, aCompCor, ICA-based denoising, Global Regression, and 0.008 to 0.09 Hz band-pass filtering). Three main comparisons will be evaluated: The effect of drug treatment on rsfMRI measures, the effect of pain intensity on rsfMRI measures (each via linear regression as in Aim 1), and the differences in rsfMRI measures between active drug responders and non-responders; this last will also be analyzed via linear regression; note, however, that this will be limited to those in the active group and people in the placebo group will not be included. First, we will evaluate region-of-interest (ROI) based functional connectivity in a set of anatomically defined regions known to be impacted in SCI and neuropathic pain: the periaqueductal gray, the bilateral thalamus, the amygdala, the hippocampus, the insula, anterior cingulate, the precentral and the post-central gyrus. Second, we will evaluate, on a voxel-by-voxel basis, amplitude of low frequency fluctuations (ALFF) and intrinsic resting state functional connectivity.

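### Removal for depression or suicidality can take worsened participants out of the two-point PHQ-9 analysis, so the 3-month mood comparison can understate harm; the weekly PHQ-9 scores should be analysed instead

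*Combined protocol and SAP*

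**What the plan says.** - **Outcome.** Section 3.2 lists psychosocial secondary outcomes "such as change in mood, satisfaction with life, and community integration". Section 15.1 names the PHQ-9 as the mood measure, "measured at baseline and again at 3-months of treatment".
- **Analysis.** Section 15.1 specifies "linear regression including terms for group and time and the interaction of group by time", stated for pain reduction; no separate between-arm model is written for mood. Mood change also enters an exploratory analysis relating "changes in pain and changes in mood, life satisfaction, resting state brain connectivity, and community integration using linear regression".
- **Removal.** The study drop criteria in Section 5.2 take participants out of the study for safety reasons that include "development of depression, aggressive behavior, anxiety, or suicidality, or evidence of brivaracetam adverse events". No PHQ-9 threshold is given.
- **Follow-up.** Section 5.2 states: "End of study assessments will be repeated 3 months after baseline testing", with a further assessment one month after the drug is stopped. Neither the text nor Table 1 describes an early-termination assessment or continued follow-up of removed participants.
- **Weekly scores.** Section 5.2 also states: "Blinded data collectors will perform weekly check-in calls to assess for medication-related adverse events including the PHQ-9 for changes in mood and suicidality". Section 15 assigns these scores no analysis.
- **Data after termination.** Section 12.3 keeps the data of terminated participants for analysis unless they ask otherwise, but names no method. Section 15 has no missing-data method.

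**The concern.** The loss of the 3-month score can depend on the outcome being measured. A participant whose depression emerges in, say, week 5 may be removed and then contribute no month-3 PHQ-9, although the weekly calls have recorded the worsening up to that point. Section 13.1 lists depression and suicidal ideation among the drug's risks, so removals may differ by arm.

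The month-3 comparison would then be made among people partly selected for not having worsened, and the pain-mood correlation would lose the same people. This matters even in a pilot. Section 15.2 gives estimation for a follow-up trial as the main purpose, and Specific Aim 1 asks whether the drug is safe. A reassuring mood result that arises from selection could carry forward into the next design.

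**Working it through.** **No figure to reproduce.** The documents give no SD, effect size, removal rate or PHQ-9 cut-off for mood. All inputs below are assumptions, used to find the direction and plausible range of the bias.

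**Step 1: closed form.** Let PHQ-9 change be normal with mean m and SD s, and suppose everyone with a change above c is removed. The mean change among those left is m − s·φ(a)/Φ(a), with a = (c − m)/s. Take s = 5, c = 5, m = 0 on placebo and m = 2 on active:
- Placebo: a = 1.0, and 0 − 5 × 0.2420/0.8413 = −1.44; removed 1 − 0.841 = 16%.
- Active: a = 0.6, and 2 − 5 × 0.3332/0.7257 = −0.30; removed 1 − 0.726 = 27%.
- Observed difference: −0.30 − (−1.44) = 1.14, against a true 2.0.

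Over s = 4 or 5, true difference 1 to 3 and c = 4 to 6 (18 combinations), 49% to 74% of the true difference remains. This calculation removes everyone above the cut and treats the triggering score as the month-3 score.

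**Step 2: simulation with partial removal.** 400,000 participants per arm; baseline about N(5, 3); change SD 3 to 5; true worsening on drug 0 to 3 points; scores bounded at 0-27. The trigger was either a rise of 5 or more, or a score of 10 or more. Half or all of those meeting it were removed before month 3. Shrinkage = 1 − estimate/(difference with everyone kept). The bound at zero makes the full-data difference slightly smaller than the nominal effect.

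| Trigger | SD | True effect | Removed of those triggered | Removed, placebo/active | Everyone kept | Estimate | Shrinkage |
|---|---|---|---|---|---|---|---|
| Rise ≥5 | 4 | 2 | half | 5%/11% | 1.78 | 1.49 | 16% |
| Rise ≥5 | 4 | 2 | all | 11%/23% | 1.77 | 1.04 | 41% |
| Rise ≥5 | 5 | 1 | half | 8%/11% | 0.84 | 0.68 | 19% |
| Rise ≥5 | 5 | 3 | all | 16%/34% | 2.60 | 1.23 | 53% |
| Score ≥10 | 3 | 3 | half | 4%/14% | 2.82 | 2.59* | 8% |
| Score ≥10 | 3 | 1 | all | 9%/14% | 0.91 | 0.74* | 19% |

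*Change among completers. The other rows use the group-by-time estimate.

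Across all scenarios with a harmful effect, shrinkage was about 8-19% with half removed and 19-53% with all removed.

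**Step 3: no drug effect.** With a rise of 5 or more, SD 4 and everyone triggered removed, each arm loses 11% and the between-arm estimate stays at about 0. The within-arm change on active moves from +0.38 to −0.39, so a slight worsening appears as an improvement.

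**Step 4: a susceptible minority.** If 10% of the active arm worsens by 8 points and all are removed, the true difference of 0.10 × 8 = 0.8 becomes 0. The chance of at least one such removal is 1 − 0.9^10 = 0.65 with 10 per arm, or 1 − 0.9^20 = 0.88 with 20 per arm. Both are shown because Section 23.1 gives 20 participants study-wide, whereas Section 5.1 gives 20 at each of two sites.

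**The case against.** **Harm is counted elsewhere.** Drug-related adverse events, screened weekly, are a primary endpoint (Section 3.1), and a medical monitor reviews adverse events monthly (Section 18.2). This stands: a reader might infer that the trial hides depression caused by the drug, and the documents do not support that. But the event count needs a judgement of relatedness and does not correct the mood comparison or the pain-mood correlation.

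**Removal need not follow a modest PHQ-9 rise.** The suicide protocol in Section 5.2 answers distress without intent to self-harm by referral and notification, and does not mention removal. Section 8.2 excludes past or current suicidality and active psychiatric treatment, so removals may be few. This also stands, and is why the half-removed range is shown.

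**Anxiety and aggression are not what the PHQ-9 scores.** Correct. Removal for these alone does not mean that a worsened PHQ-9 is lost. The direct link is through depression and suicidality.

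**Section 12.3 says collected data will be analysed, and no passage forbids a month-3 questionnaire after removal.** Both are true, so it goes too far to say that the weekly scores will never be used or that every removed person lacks a month-3 value. But a baseline-and-3-month analysis has no place for a score taken between those times, and removal from the study makes loss of the later one likely.

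**This is a small pilot.** That argues for a simple model, not for leaving out scores already collected.

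**Conclusion.** The concern holds in conditional form. The month-3 mood comparison and the pain-mood correlation can exclude participants whose mood worsened. The between-arm difference is understated if mood-related removals are more frequent on active drug. With equal removals and no drug effect it is about unbiased, although within-arm change is flattered.

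A reader might infer that the plan necessarily understates harm, or that a quarter to a half of the effect is hidden. Neither is supported. The first needs unequal removal. The second needs an assumed cut-off with everyone above it removed, and removing half gives only about 8-19%. The wider 19-53% range describes full removal, and both ranges rest on assumed SDs, effects and triggers. The true size cannot be derived from the documents.

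**What to change.** Leave the removal rule unchanged. In Section 15.1:

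1. Analyse change in mood from all weekly PHQ-9 scores of all randomised participants, up to and including the call that leads to removal. Use a repeated-measures model with arm, time, arm-by-time and baseline, kept simple for 10-20 per arm.
2. Report mood-related removals by arm beside that result.
3. Label the 3-month completer comparison as supportive.
4. If the largest rise from baseline is shown, keep it descriptive and note that it depends on how many weeks each person was followed.

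The cost is analysis wording and a modest amount of extra analysis. The revision history records enrolment as complete, and the change needs only scores the plan already collects. There are two downsides to state. The model assumes data are missing at random after removal, which is weaker where removal rests on something the PHQ-9 does not record. Telephone scores also differ in mode from visit questionnaires.
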